We will explore cohorts defined by both FGFR1 gene copy number alterations and by FGFR1 mRNA levels, both of which appear as non-completely overlapping predictive biomarkers of ponatinib sensitivity, with the suggested cutpoint for positive set by preclinical cell line data. In addition, we will explore cohorts defined by FISH as positive for a RET rearrangement. As ponatinib has greater potency against RET than FGFR1, in order to mitigate risks relating to ponatinib exposure, the known RET positive cohort will be treated at 30mg. We are aiming to explore each biomarker selected cohort using a single stage design looking for preliminary evidence of a high response rate ($\geq 40\%$), reserving further confirmation for additionally supported cohort expansions or standalone studies in the future. We also include a pan-negative cohort which will be treated at 45mg.

Primary biomarker studies will be conducted prospectively as part of the screening, however excess pre-therapy tumor samples plus optional post-therapy rebiopsy samples in cases of acquired resistance after initial sensitivity will be banked to permit additional retrospective analyses. In addition, baseline germline DNA and baseline, on-study and end-of-study plasma will also be banked to permit later analyses looking for additional markers of sensitivity, toxicity or resistance.

FGF2 and FGF9 ligand mRNA levels in the FGFR1 cohorts, and the impact of higher FGFR1 mRNA levels, copy number or specific patterns of copy number gained will be assessed retrospectively in FGFR1+ cohorts to see if, in conjunction with the primary biomarker in the same pathway, they can act as additional discriminators of clinical benefit. Other biomarkers, e.g. of ponatinib targets unrelated to the pathway of the primary biomarker of a cohort, will be assessed retrospectively in a discovery approach directed towards 'atypical' responders (responders in the FGFR1 marker negative cohort or responders in marker positive cohorts where there are only 1-2 responders out of 12 evaluable patients, but is not explicable by the presence of RET or more stringent FGFR1/FGF criteria). These retrospective analyses will generate hypotheses to be explored in future work.

This is an open-label phase II study in lung cancer involving two parts:

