The effectiveness of prescreening will be summary measures. Success of the nationwide approach will be defined by 50% of screening enrollments coming from outside Colorado, with 85% of marker positive patients enrolling into available cohorts of the intervention trial. No formal hypothesis testing will be performed. Summary statistics such as percentage and its 95% CI will be used to track and analyze the remote patients and local patients capture and enrollment as well as the barriers to remote patient accrual. Analyses contrasting remote outreach methodology with the numbers and proportions seen through traditional direct clinical contact will be descriptive in nature.

Part B Analysis Plan:

Sample size consideration:

The clinical trial will employ a one-stage design (A'Hern, 2001). In each molecularly defined positive cohort, the study requires 12 subjects to decide whether the ORR is greater than or equal to 0.400 assuming the response rate is 0.050 without treatment. 12 subjects will provide over 90% power to detect this rate difference with a targeted type I error rate of 0.05 and an actual error rate of 0.02. If the number of responses is 3 or more, the hypothesis that $P \leq 0.05$ (null hypothesis) is rejected. If the number of responses is 2 or less, the hypothesis that $P \geq 0.40$ is rejected. Note, given the exploratory nature of this phase II clinical trial, p-values will not be adjusted for multiple outcomes in the primary objective.

We will also include a pan-negative cohort of 20 patients to compare the ORR between each positive cohort and the negative one as secondary objectives. The ORR response differences between each biomarker positive cohort and the negative cohort will be evaluated using Fisher's exact test with a descriptive p-value. For *FGFR1* SISH+ or ISH+, the positive cohorts will also be combined for more power when comparing to the negative cohort. The response rates in different molecularly defined cohorts and different dose cohorts will be summarized using binomial proportions with 95% exact binomial confidence intervals. Differences among cohorts will be evaluated using Fisher's exact test with a descriptive p-value.

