2.2.2 Updated long term risks associated with ponatinib use

Arterial and venous thrombosis and occlusions, including fatal myocardial infarction, stroke, stenosis of large arterial vessels of the brain, severe peripheral vascular disease, and the need for urgent revascularization procedures have occurred in at least 27% of ponatinib-treated patients from the phase 1 and phase 2 trials. Ponatinib can cause fatal and life-threatening vascular occlusion within 2 weeks of starting treatment. Ponatinib can also cause recurrent or multi-site vascular occlusion.

In the dose-escalation (phase 1) clinical trial, 48% (31/65) of patients with CML or Ph+ ALL developed vascular occlusive events. The median time to onset of the first vascular occlusion event was 5 months.

Ponatinib can cause fatal and life-threatening vascular occlusion in patients treated at dose levels as low as 15 mg per day. Patients with and without cardiovascular risk factors, including patients age 50 years or younger, experienced these events. Vascular occlusion adverse events were more frequent with increasing age and in patients with prior history of ischemia, hypertension, diabetes, or hyperlipidemia.

Arterial Occlusion and Thrombosis

Arterial occlusion and thrombosis occurred in at least 20% (91/449) of Ponatinib-treated patients with some patients experiencing events of more than one type. Patients have required revascularization procedures (cerebrovascular, coronary, and peripheral arterial) due to vascular occlusion from Ponatinib. Cardiac vascular occlusion, including fatal and life-threatening myocardial infarction and coronary artery occlusion has occurred in 12% (55/449) of Ponatinib -treated patients, Patients have developed heart failure concurrent or subsequent to the myocardial ischemic event.

Cerebrovascular occlusion, including fatal stroke has occurred in 6% (27/449) of Ponatinib -treated patients. Ponatinib can cause stenosis over multiple segments in major arterial vessels that supply the brain (e.g., carotid, vertebral, middle cerebral artery).

Peripheral arterial occlusive events, including fatal mesenteric artery occlusion and life-threatening peripheral arterial disease have occurred in 8% (36/449) of Ponatinib -treated patients. Patients have developed digital or distal extremity necrosis and have required amputations.

Venous Thromboembolism

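### No biomarker-positive cohort has a futility stop based on its own responses; closing enrolment at 0 responses in 8 would cost about 0.3 points of power

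*Combined protocol and SAP*

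**What the plan says.** The overview describes cohorts explored "using a single stage design looking for preliminary evidence of a high response rate", and the Part B Analysis Plan (synopsis and Section 10.3) names the method: "The clinical trial will employ a one-stage design (A'Hern, 2001". The sizing reads "In each molecularly defined positive cohort, the study requires 12 subjects"; it sets a target rate of 0.40 against a null rate of 0.05. The null is rejected "If the number of responses is 3 or more". The operating characteristics given are a "targeted type I error rate of 0.05 and an actual error rate of 0.02" and "12 subjects will provide over 90% power to detect this rate difference". The only interim analyses set by number are in Part A, at 250 and 500 screened samples.

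Early data are used in other ways:
- **Pooled pharmacodynamic look.** Section 4.0 has the first 12 patients across all cohorts analysed for FGFR pathway effect before more are enrolled. The stated consequence concerns which doses are explored.
- **Tolerability.** Section 9.3 calls a dose non-tolerated at 3 or more dose-limiting toxicities.
- **Pooled suspension.** Section 9.3 suspends FGFR1+ accrual if neither pathway modulation nor clinical benefit is seen at any achievable dose.
- **Oversight.** Section 11.9 has responses discussed at working-group meetings and summarised quarterly to the safety committee, which can close the trial for safety or conduct reasons.

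On risk, the section on updated long-term risks (the second one numbered 2.2.2) says that vascular occlusive events "have occurred in at least 27% of ponatinib-treated patients from the phase 1 and phase 2 trials".

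**The concern.** A positive cohort whose first 8 evaluable patients show no response has no rule of its own that closes it. The pooled rule in Section 9.3 does not reach it if plasma FGF23 rises in enough patients or if a different FGFR1+ cohort responds, and it does not apply to RET+ at all. The cohort can then go on enrolling to 12, although it would need at least 3 responses in the last 4 patients to succeed.

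The stake is exposure of new patients. Section 2.3 weighs the vascular risk by noting a median onset of 5 months against a first efficacy assessment at 8 weeks, so that those who continue are judged to be benefiting. That argument covers patients already on treatment. It does not cover those entering a cohort that has shown no activity, and the section on long-term risks also says that occlusion can occur within 2 weeks. The mitigations listed there concern dose, eligibility and prophylaxis; the response design is not among them.

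**Working it through.** **Inputs.** From Section 10.3: 12 evaluable patients per positive cohort, success at 3 or more responses, null rate 0.05, target rate 0.40. From Section 5.5: 85% of marker-positive patients enter treatment, and Table 10 gives the accrual. From Section 7.4: scans about every 8 weeks. The 0-of-8 look is this review's proposal and is not in the plan.

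**1. The plan's own figures.** With X binomial on 12 patients:
- Type I error = 1 − (0.95^12 + 12×0.05×0.95^11 + 66×0.05²×0.95^10) = 1 − (0.5404 + 0.3413 + 0.0988) = 0.0196.
- Power = 1 − (0.6^12 + 12×0.4×0.6^11 + 66×0.4²×0.6^10) = 1 − (0.0022 + 0.0174 + 0.0639) = 0.9166.

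Both agree with the printed 0.02 and over 90%.

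**2. Adding the look.** The only successes lost are those with 0 of 8 followed by at least 3 of 4.
- At 40%: P(at least 3 of 4) = 4×0.4³×0.6 + 0.4^4 = 0.1792, and 0.6^8 = 0.0168. The loss is 0.0168 × 0.1792 = 0.0030, so power is 0.9135 (0.914 from unrounded terms).
- At 5%: P(at least 3 of 4) = 0.00048, and 0.95^8 = 0.663. The loss is 0.0003, so type I error is 0.0192.
- The exact 95% upper limit at 0 of 8 is 1 − 0.025^(1/8) = 0.369, below 0.40.

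**3. Choice of look.** Same calculation, same final rule:

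| Stop if | Power |
|---|---|
| 0 of 6 | 0.895 |
| 0 of 7 | 0.908 |
| 0 of 8 | 0.914 |
| 1 or fewer of 8 | 0.867 |

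**4. How often it stops.** (1 − p)^8 gives 0.663 at a response rate of 5%, 0.430 at 10%, 0.168 at 20% and 0.017 at 40%. At 5% the expected number of evaluable patients is 8 + 4×(1 − 0.663) = 9.35 instead of 12. Over four cohorts at 5%, 4×4×0.663 = 10.6 fewer, if enrolment pauses for the look.

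**5. Without a pause.** Patients entering during the 8 weeks to the scan = yearly positives × 0.85 × 8/52, using the highest yearly totals in Table 10 (internal plus external). The saving is (4 − that number) × 0.663.

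| Cohort | Positives per year | Enter in 8 weeks | Expected saving at 5% |
|---|---|---|---|
| SISH+ISH+ | 10 | 1.3 | 1.8 |
| SISH+ISH− | 16 | 2.1 | 1.3 |
| SISH−ISH+ | 28 | 3.7 | 0.2 |
| RET+ | 6 | 0.8 | 2.1 |

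The total is 5.4, about 5. With all four at 10% the figures are 6.9 with a pause and 3.5 without.

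**6. Responses seen only after the look.** The documents give no late fraction L, so a range is shown. Power lost = sum over h of C(8,h) × (0.4L)^h × 0.6^(8−h) × P(at least 3−h of 4 at 0.4), where h counts responders among the 8 not yet visible.

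| L, applied to all 8 | 0 | 10% | 16% | 20% | 30% |
|---|---|---|---|---|---|
| Power | 0.914 | 0.907 | 0.900 | 0.894 | 0.873 |

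With staggered entry most of the 8 will have had more than one scan. If only the last 2 are affected, power is 0.911 at 20% and 0.909 at 30%.

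**The case against.** The one-stage design is a declared and correctly sized choice for preliminary evidence, so this is not the correction of an error. That stands. Four further points deserve an answer.

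- **Early results are not ignored.** A reader might infer that every cohort is filled to 12 whatever happens. The documents do not support that: the pooled pharmacodynamic look, the toxicity rule, the pooled FGFR1+ suspension and the safety committee can each halt or redirect enrolment. None of them sets a response criterion for a single cohort, so the narrower gap remains.
- **Late responses and confirmation.** Section 10.4 makes best response depend on confirmation as well as measurement. If only confirmed responses counted at the look, recent responders would be read as failures. This stands as a requirement on the wording of the rule. It does not defeat the rule, because power stays at 0.90 or more until about 16% of responses in all 8 patients are still unseen.
- **The result is not certain at 0 of 8.** A cohort with a true rate of 40% would still succeed 17.9% of the time from there. That is correct, but such a cohort reaches 0 of 8 only 1.7% of the time, hence the small loss of power.
- **The gain is modest, and some information is lost.** Without a pause about 5 of 74 planned patients are spared, and only if all four cohorts are inactive. A stopped cohort gives 8 patients instead of 12 to its confidence interval, to the pooled FGFR1+ comparison with the negative cohort, and to the planned work on atypical responders (Section 2.6). This stands as the price.

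**Conclusion.** The point holds as a cheap improvement to a valid design. No positive cohort has its own response-based futility stop, and the pooled suspension in Section 9.3 does not replace one. A look at 0 of 8 leaves the plan's stated error rate of 0.02 and power over 90% true (0.0192 and 0.914). It cuts expected enrolment in a cohort at 5% from 12 to 9.35 evaluable patients. Across four such cohorts that is 10.6 patients with a pause or about 5 without, and almost none of the latter in SISH−ISH+.

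This assumes that at most about 16% of responses in all 8 patients are still unseen at the look, that unconfirmed responses count, and that accrual follows Table 10.

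A reader might multiply the 27% vascular figure by the patients spared to obtain events avoided. The documents do not support that. The figure comes from the earlier haematological trials, before this protocol's vascular exclusions, and has no stated exposure period. It shows that the risk is serious; it does not measure the benefit of the look.

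**What to change.** In Section 10.3 and the synopsis, add a non-binding look for each positive cohort. When the 8th evaluable patient at the dose being analysed has had the first post-baseline scan, close enrolment to that cohort if none of the 8 has a RECIST response. Count unconfirmed responses as responses at this look, and allow continuation where shrinkage is emerging. The rule concerns enrolment only. Keep 3 of 12 as the success rule, restate type I error as 0.019 (still below 0.02 if the look is overridden) and power as 0.914, and give the late-response range from the working.

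Three matters need a sentence each:
- whether enrolment pauses while the scan is awaited, which decides most of the saving in SISH−ISH+;
- how a stop at 0 of 8 is to be reconciled with the Section 9.3 provision that follows 2 or fewer responses in the initial RET+ cohort;
- how the first 8 are counted after a change of dose, given that Section 10.3 and the synopsis restrict each cohort to patients treated at the final dose.

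The cost is protocol wording, 0.3 points of power (about 1 point if 10% of responses are late, 2 points at 20%), and the smaller numbers in a stopped cohort. No extra scans or patients are needed.

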1. OBJECTIVES

Ponatinib is a multi-targeted tyrosine kinase inhibitor with known activity against several different kinases of potential importance in lung cancer. With the advent of molecularly specific licensing opportunities and proven evidence of activity of key tyrosine kinase inhibitors (TKIs) given to biomarker-selected subgroups of non-small cell lung cancer (NSCLC) our goal is to prospectively define highly sensitive molecular subgroups for ponatinib. As ponatinib has activity against several different kinases, and each kinase may have several different potential predictive biomarkers associated with it, reflecting either different, non-overlapping, mechanisms of activation and/or overlapping markers associated with the same mechanism of activation, we aim to explore several different molecularly defined subgroups for the same drug, including multiple markers for the same pathway. Ponatinib is, in part, an FGFR inhibitor.

Exposures at the standard dose of 45mg QD are predicted to be sufficient to affect FGFR1 in vivo, but we will prove this through normal tissue biomarker exploration in the first 12 patients (across all 45mg cohorts). Due to new data relating to longterm vascular risks with ponatinib (see section 2.2.2), if exposures are inadequate to affect these biomarkers and no evidence of tumor shrinkage is seen in the FGFR1 selected cohorts at that point, higher doses will not be explored. In addition, inclusion and exclusion criteria have been modified to mitigate risk and in patients who are not already on a statin or anticoagulation, low dose aspirin (81mg) and statin (eg 10mg atorvastatin) prophylaxis is recommended, in the absence of contraindications.

We will explore cohorts defined by both FGFR1 gene copy number alterations and by FGFR1 mRNA levels, both of which appear as non-completely overlapping predictive biomarkers of ponatinib sensitivity, with the suggested cutpoint for positive set by preclinical cell line data. In addition, we will explore cohorts defined by FISH as positive for a RET rearrangement. As ponatinib has greater potency against RET than FGFR1, in order to mitigate risks relating to ponatinib exposure, the known RET positive cohort will be treated at 30mg. We are aiming to explore each biomarker selected cohort using a single stage design looking for preliminary evidence of a high response rate ($\geq 40\%$), reserving further confirmation for additionally supported cohort expansions or standalone studies in the future. We also include a pan-negative cohort which will be treated at 45mg. Primary biomarker studies will be conducted prospectively as part of the screening, however excess pre-therapy tumor samples plus optional post-therapy rebiopsy samples in cases of acquired resistance after initial sensitivity will be banked to permit additional retrospective analyses. In addition, baseline germline DNA and baseline, on-study and end-of-study plasma will also be banked to permit later analyses looking for additional markers of sensitivity, toxicity or resistance.

FGF2 and FGF9 ligand mRNA levels in the FGFR1 cohorts, and the impact of higher FGFR1 mRNA levels, copy number or specific patterns of copy number gained will be assessed retrospectively in FGFR1+ cohorts to see if, in conjunction with the primary biomarker in the same pathway, they can act as additional discriminators of clinical benefit. Other biomarkers, e.g. of ponatinib targets unrelated to the pathway of the primary biomarker of a cohort, will be assessed retrospectively in a discovery approach directed towards 'atypical' responders (responders in the FGFR1 marker negative cohort or responders in marker positive cohorts where there are 1-2 responders out of 12 evaluable patients, but is not explicable by the presence of RET or more stringent FGFR1/FGF criteria). These retrospective analyses will generate hypotheses to be explored in future work.

This is an open-label phase II study in lung cancer involving two parts:

Part A involves the prospective prescreening of tumor samples from patients with lung cancer to identify patients who are positive for one, or more than one, of a series of different biomarkers potentially predictive of radiographic responses from ponatinib. Using a novel approach increasing prescreen awareness through the internet and the use of remote consenting for molecular testing over the phone to minimize unnecessary travel in some patients, we hope to be able to screen nationally and then invite patients with relevant marker results to visit CU for screening for interventional trial enrollment in Part B. Patients with all histologies (NSCLC and SCLC) other than carcinoid will be screened for FGFR1 copy number by silver in-situ hybridization (SISH) and for FGFR1 mRNA levels by in-situ hybridization (ISH). Patients with adenocarcinoma or not-otherwise-specified (NOS) histologies who are negative for both FGFR1 SISH and ISH will be screened by RET FISH when covered as SOC. CU internal cases tested by RET FISH will also have been pre-selected to be ‘pan-negative’ by SNaPshot and ALK/ROS1/MET FISH (or equivalent). Patients who sign the consent for trial-specific molecular prescreening (Part A) will also allow the investigators retrospective and prospective access to their medical records to capture the features that may be associated with either positive or negative biomarker results. These factors will include but not be limited to age at diagnosis of current lung cancer, age at diagnosis of metastatic lung cancer (if different), sex, race, histology, current stage, sites of metastatic disease at diagnosis, smoking status, other known molecular features such as EGFR, KRAS and ALK status and overlap of any trial specific positive biomarker results. In addition, the consent will permit capture of information relating to the patient’s prior therapies and outcomes from these therapies (response and progression free survival (noting the method and frequency of radiographic assessment)), and overall survival from the date of diagnosis of metastatic disease. We will then analyze both the clinical and demographic features associated with positivity, as well as any suggestion of a marker specific responsiveness/non-responsiveness to specific standard therapies as we have done before (Camidge et al, 2010; Camidge et al, 2011; Doebele, Lu et al, 2012).

Part B involves treating a series of molecularly defined lung cancer cohorts (FGFR1 SISH+ISH+, FGFR1 SISH+ISH-ve, FGFR1 SISH-veISH+, FGFR1 SISH-veISH-ve (FGFR1 double negative cohort) and RET FISH+) with standard dose ponatinib looking at the objective response rate in each cohort as evidence of the predictive utility of the biomarker for this drug. Evidence that 45mg QD of ponatinib achieves systemic exposures high enough to affect wildtype FGFR pathway function in the host will be sought from the first 12 patients accrued in total across all cohorts and analyzed prior to additional enrollment. If no evidence of host pathway modulation is apparent AND no evidence of clinical responses have been seen in the FGFR1+ cohorts, further exploration of higher doses/exposure regimens will not be undertaken. If there is clear evidence of activity at 45mg, even if well tolerated, potentially lower doses (eg 30mg) may also be explored in the FGFR1 cohorts to mitigate safety in future studies. The National Cancer Institute Common Terminology Criteria for Adverse Events (NCI-CTCAE, Version 4.0) will be used to grade adverse events. A dose level will be considered tolerable following completion of 1 cycle (28 days) in 9 of 12 patients in the absence of dose limiting toxicity (DLT). If ≥ 3 patients experience DLT at this dose level, the dose level will be deemed non-tolerated. A DLT will be defined by the adverse events listed in Section 9 that are considered possibly, probably, or definitely related to ponatinib. If 45mg is not tolerated per DLT criteria, 30mg will be explored in the FGFR1 cohorts, assuming insufficient patients were treated at 45mg to assess efficacy accurately. As the IC50 for RET is an order of magnitude lower than for FGFR1, and the starting dose for the RET cohort will be 30mg, the logic relating to efficacious exposures for doses based on FGFR1 PD markers/responses will not automatically be applied to the RET+ cohort and if activity in RET+ cases is noted at the time this will not influence the decision-making re dose alteration in the FGFR1+ cohorts. However, if ≤ 2

responses are seen in the initial RET+ cohort but FGFR1+ responses or FGFR PD modulation have been noted at 45mg and 45mg appears acutely well tolerated per DLT criteria we will reconsider this logic and accrue an additional RET+ cohort at 45mg. If doses other than 45mg QD are explored, the number of patients in each biomarker selected cohort will be modified to include only those treated at the final ‘biologically selected dose’ (i.e. the tolerable dose associated with evidence of FGFR pathway pharmacodynamic modulation or of radiographic responses in FGFR biomarker selected cohorts) and the response rates in each biomarker selected cohort will be calculated within each cohort using only the number treated at this dose.

Objectives:

Primary:

Part A – To determine the prevalence of defined biomarkers in the screened patient populations.

Part B – To determine the objective response rate (ORR) (RECIST v1.1) to ponatinib at a ‘biologically selected dose’ in different molecularly defined cohorts of lung cancer.

Secondary:

Part A –

- 1) To determine the effectiveness of prescreening locally and nationally.
- 2) To determine the clinical and pathological features associated with biomarker positivity and negativity.

Part B –

- 1) To evaluate the safety, tolerability, and adverse event profile of ponatinib in patients with advanced lung cancer.
- 2) To determine the progression free survival (PFS), pattern of failure (CNS vs. extra-CNS) and response duration (in patients who achieve an objective response) of ponatinib in molecularly defined cohorts of patients with advanced lung cancer treated at the ‘biologically selected dose’.
- 3) To compare the ORR in biomarker positive cohorts to the FGFR1 double negative cohort.

Tertiary/Exploratory:

- 1) To explore additional molecular mechanisms of initial sensitivity and resistance to ponatinib in patients with advanced lung cancer, including but not limited to addressing the impact of higher cutpoints/alternate patterns of FGFR1 copy number by SISH and mRNA levels by ISH on maximal percentage shrinkage per RECIST or PFS or duration of response in the FGFR1 copy number and/or mRNA positive cohorts; and the impact of FGF2 and/or 9 ligand mRNA levels by ISH on maximal percentage shrinkage per RECIST or PFS or duration of response in FGFR1 copy number and/or mRNA positive cohorts.
- 2) To explore the molecular mechanisms of acquired resistance to ponatinib in patients with advanced lung cancer who initially benefited (minor or objective responses, or stable disease ≥ 6 months on therapy) but then progressed, including but not limited to looking at changes in tumor or host biology comparing pre-treatment with available post-progressing tumor and/or other biological samples.

